### **Problem Statement:**

Currently, AMD is among the top three leading causes of vision loss in veterans (Chomsky et al., 1995; Quillen & Henry, 2000). A recent survey found that 67% percent of individuals enrolled in low-vision rehabilitation programs had AMD (Owsley et al., 2009). Vision losses associated with this disease increase with age, and its impact on veterans' health care will dramatically increase as the number of older individuals is expected to double in the next ten years. In the United States, cases of early AMD are expected to double from 9.1 million to 17.8 million by 2050 (Rein et al., 2009).

The deficits in visual function as a result of diseases affecting the central retina, including AMD, are debilitating, as individuals lose their ability to carry out many of their daily activities that require resolving fine spatial details (Szlyk et al., 1997; 1998a; 2001a; 2001b; Ardickas et al., 2002; Stelmack et al., 2002). Often, individuals with poor central vision lose self-esteem and are subject to depression due to their inability to function normally in everyday life (Szlyk et al., 1998b; 2000a; Brody et al., 2001; Grant, Seiple & Szlyk, 2011).

As central visual acuity becomes progressively worse, a parafoveal locus for fixation, or preferred retinal locus (PRL), may be chosen because it provides better vision than the diseased fovea (Timberlake et al., 1986, 2006; Fletcher et al., 1999; Crossland et al., 2005;). Although reading speeds using a PRL are typically slower than with foveal vision, there are reports that the visual function of patients with macular disease can benefit from rehabilitation training (Watson & Jose, 1976; Nilsson & Nilsson, 1986; Nilsson, 1990; Frennesson et al., 1995; Hall & Ciuffreda, 2001). Many of the vision rehabilitation programs for these patients focus on eccentric viewing training and the use of optical magnifying devices (Goodrich & Quillman, 1977; Quillman, 1980; Maplesden, 1984; Nilsson & Nilsson, 1986; Nilsson, 1990; Frennesson et al., 1995; Nilsson et al., 1998, 2003). Such programs have individual exercises that explicitly and implicitly train visual skills with the goal of improving reading performance. Many of the published studies have reported increases in reading speeds as a result of training with low-vision devices, as well as maintenance of these skills and continued device usage following training (Watson et al., 1997). A different approach to reading rehabilitation emphasizes the training of oculomotor control relative to a new extrafoveal fixation locus (Solan et al., 1995; Hall & Ciuffreda, 2001; Contestabile et al., 2002; Seiple, Szlyk et al., 2005, 2011).

Our previous studies have shown that training with oculomotor control exercises results in significantly faster reading speeds in patients with AMD. All of our past work was conducted under controlled laboratory conditions. In the proposed study, we will examine whether these training exercises are effective when practiced at home. Because of the extensive cost of clinical resources required for vision rehabilitation and the significant number of veterans in need of services, it is critical to determine whether the training program can be made less expensive, but as effective when the program is self-trained.

## **Key Questions:**

The key question of this proposed research project is whether a series of eye movement training exercises that we have validated in our laboratory environment can be translated into a home-based training system.

The primary question that this research is designed to answer is: Can a home-based eye movement training program be as effective as a clinically administered program? In order to answer this question, we will assess whether the opportunity for increased practice afforded by having the program available at home results in improved reading performance.

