# Phase 2 - Clinic-Based Versus Home-Based Training

In this phase, we will compare reading outcomes from training with PAECT in a low-vision clinic setting and with feedback on performance given by a rehabilitation therapist to training with the PAECT by the patients in their own homes. We have previously demonstrated in our laboratory experiments that eye movement training exercises increase reading speed, but we wish to know whether these findings can be extrapolated to clinical practice. The results of this study will allow us to quantify the role of direct support and feedback from the therapist during each session versus any advantages that may result from more frequent practice on the exercises afforded by having the equipment at home.

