# **Procedure**

On Day 1 of the study, all patients will undergo clinical assessments to measure change in reading speed (MNREAD). Near refraction will be measured and, based on this, a pair of single vision spectacles will be made for each subject for testing purposes. On Day 2, all patients will return to the clinic for baseline assessments detailed instructions on running the PAECT platform and training on Module 1 of the platform. For those patients assigned to the clinical arm of the study, appointments will be made to

return at weekly intervals for two-hour PAECT training sessions. During these sessions, the subjects will run the PAECT program in the clinic, with feedback and encouragement given by the therapist.

There will be a total of *eight training sessions*. For those patients assigned to the At-home arm, arrangements will be made to deliver and set up a computer in their home. These subjects will be instructed to practice with the PAECT program as often as possible, but at least two hours per week. Patients will receive weekly from calls from the Program Coordinator, who will answer technical questions and encourage frequent use of the program, but no feedback about performance will be given. All patients in both arms will return to the clinic after one month, and two months to undergo assessments of reading performance. Each subject will participate in the study for 12 weeks: 1 screening visit, 1 baseline testing visit, 4 weeks of training, Month 1 assessment visit, 4 weeks of additional training, and a final assessment visit.

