# **Research Design and Statistical Analysis Plan**

We will recruit eligible patients per year for each of the three years for Phase 2 of the study to be assigned randomly to the Laboratory Group, while others will be assigned to an At-home Training Group. Three assessments will be taken for each subject: at

baseline, and after 1 and 2 months. To analyze the assessment data, we will utilize a two-way (group by time) repeated measures design. A major advantage of this design is subject homogeneity; that is, subject effects are reduced.

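### The primary question asks whether home training is as effective as clinic training, but the analysis plan has no rule that could support that conclusion unless home is shown superior.

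*Combined protocol and SAP*

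**What the plan says.** Key Questions labels as primary: "Can a home-based eye movement training program be as effective as a clinically administered program"? The Problem Statement gives the reason, which is cost: "it is critical to determine whether the training program can be made less expensive, but as effective when the program is self-trained". Both look for effectiveness that is retained in a cheaper setting.

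The sentence after the primary question describes the means of answering it: "we will assess whether the opportunity for increased practice afforded by having the program available at home results in improved reading performance". Methods of Procedure adds only that reading outcomes in the two settings will be compared.

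For the analysis, the Research Design and Statistical Analysis Plan says "we will utilize a two-way (group by time) repeated measures design", with assessments at baseline, 1 month and 2 months. It mentions one advantage of the design and ends. It does not state a hypothesis, a primary contrast, a margin, a confidence-interval rule, or which result would count as equally effective.

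On the comparator, the Problem Statement says "All of our past work was conducted under controlled laboratory conditions". The Phase 2 section still treats transfer as open: "we wish to know whether these findings can be extrapolated to clinical practice".

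**The concern.** The group-by-time test takes as its null that the two groups change in parallel. Rejecting it in favour of home would answer the primary question positively. Failing to reject it is not evidence of parallel change, because an imprecise comparison also fails to reject when home is materially worse. If the two settings perform about equally well, which is the result the cost argument needs, the plan as written cannot validly say so.

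There is a secondary weakness. Two arms can look alike because neither improved. Since benefit in the clinic setting is itself an open question in this protocol, similarity between arms is informative only if the clinic arm is seen to improve.

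**Working it through.** **The text.** The sentence on increased practice can be read in two ways. If improved means better than clinic, it covers only the superiority case. If it means better than baseline, it does not compare the arms. Neither reading supplies a rule for concluding that home is as effective when superiority is not shown.

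**Inputs.** The plan has no figure of its own to reproduce. All of the following are assumed: n patients per arm (1:1), between-patient SD 1, compound symmetry with correlation ρ between visits, two-sided alpha 0.05, a clinic gain of 0.5 SD by Month 2, and any home deficit building up linearly over the visits.

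**1. How often the planned interaction test misses a true deficit.** With d the home-minus-clinic differences at the three visits and S = Σ(d − mean d)², the 2-df test has noncentrality λ = (n/2)·S/(1 − ρ), on 2 and 2(2n − 2) degrees of freedom.

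| Scenario | d | n, ρ | λ | Non-significant |
|---|---|---|---|---|
| Home delivers half the gain | 0, −0.125, −0.25 (S = 0.03125) | 60, 0.7 | 30 × 0.03125/0.3 = 3.125 | about 67% |
| Home delivers none of the gain | 0, −0.25, −0.5 (S = 0.125) | 60, 0.7 | 30 × 0.125/0.3 = 12.5 | about 11% |
| Half the gain, small and noisy trial | S = 0.03125 | 20, 0.6 | 10 × 0.03125/0.4 = 0.78 | about 89% |
| Half the gain, large and precise trial | S = 0.03125 | 100, 0.9 | 50 × 0.03125/0.1 = 15.6 | about 5% |

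The result depends heavily on inputs that the documents do not give. What does not depend on them is that a non-significant result has no fixed meaning until the precision is reported.

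**2. What a margin rule would do on the same inputs** (n = 60, ρ = 0.7, illustrative margin 0.25 SD, equal true gains in both arms, normal approximation).

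- Difference in change, baseline to Month 2: SE = √(2 × 2(1 − ρ)/n) = √(1.2/60) = 0.141. The rule is met with probability Φ(0.25/0.141 − 1.96) = Φ(−0.19), about 42%.
- Difference adjusted for baseline as a covariate: SE = √(2(1 − ρ²)/n) = √(1.02/60) = 0.130. The rule is met with probability Φ(0.25/0.130 − 1.96) = Φ(−0.04), about 48%.
- Patients per arm for 80%: 1.2 × (1.96 + 0.842)²/0.25² = about 151 for the change contrast; 1.02 × (1.96 + 0.842)²/0.25² = about 128 with baseline as covariate.

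The two standard errors differ because these are different models. In the planned two-way design baseline is one of the three time levels, so the contrast that it naturally gives is the difference in change.

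**3. Why the clinic arm's own change matters.** The probabilities in step 2 depend only on the difference between arms. They are therefore the same, 42% and 48%, if neither arm improves at all. If the clinic arm's 95% lower limit for change must also exceed zero, the chance of a false claim in that case is at most 2.5%.

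**The case against.** The strongest reply is that the protocol does say how it will answer the question, namely by looking for an advantage from extra home practice. The Phase 2 section also anticipates such an advantage. Read as superiority of home over clinic, a group-by-time analysis fits, and a win for home would settle the matter. That stands, and the point is confined to the case where superiority is not shown.

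Second, the Phase 2 section says the results will quantify the role of therapist feedback against that of more frequent practice, which is an estimation aim, and nothing limits reporting to a p-value. This is fair, but an intention to quantify does not say which estimate would count as equally effective.

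Third, Methods of Procedure promises a large sample, so the low-precision scenarios may not apply. That is possible. The number to be recruited is absent from the text available and may have been lost, so its absence is not counted as a fault and no claim is made that the trial is small.

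Fourth, the allocation sentence reads "assigned randomly to the Laboratory Group, while others will be assigned to an At-home Training Group", and the laboratory is where earlier benefit was reported, so the comparator may be less doubtful than suggested. The Phase 2 section nevertheless places this arm in a low-vision clinic and asks whether the laboratory findings carry over.

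A reader might infer that the sponsor intends to declare the programs equal if the interaction is non-significant. The documents do not say so; they are silent on how such a result would be read.

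**Conclusion.** The concern holds within bounds. The stated primary question calls for a non-inferiority type of conclusion, and the planned analysis can reach it only through superiority. In every other case the text available offers no valid rule. The analysis text that is present runs continuously and shows no gap where a margin or rule would have stood.

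This conclusion rests on the wording and not on any figure. The illustrative size runs from about 67% non-significant for a true 0.25 SD deficit to about 11% for a 0.5 SD deficit, both at an assumed 60 per arm and correlation 0.7. It would not be right to infer that the trial is unable to detect an inferior home program. On those inputs it would usually detect a complete loss of benefit; whether it could detect a partial loss depends on figures that the documents do not give.

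It should be settled before any between-arm comparison, because a margin chosen afterwards would carry little weight.

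**What to change.** In the Research Design and Statistical Analysis Plan:

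1. State the hypothesis type. Non-inferiority matches the primary question. If superiority or estimation is what is meant, reword the question instead.
2. Name one primary contrast: the home-minus-clinic difference in change in MNREAD reading speed from baseline to Month 2, from the planned repeated measures model, with a two-sided 95% CI. If a baseline-adjusted difference is preferred, specify a model with baseline as a covariate.
3. Before any between-arm comparison, fix a margin in MNREAD units, justified by the sponsor. Conclude that home is as effective only if the lower confidence limit lies above minus the margin. Otherwise report the estimate and interval without that claim. State that a non-significant group-by-time term is not evidence of equal effectiveness.
4. Report the clinic arm's own change from baseline with a CI, and do not claim equal effectiveness if that arm did not improve.

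The wording itself needs no new visits or procedures. The price is that the result may often be inconclusive: on the assumed inputs a 0.25 SD margin is met only 42% to 48% of the time under true equality, and reaching 80% would take about 151 or 128 patients per arm depending on the model. If the planned size cannot support a justifiable margin, reword the question as estimation and report the interval.

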### **Methods of Procedure:**

Our previous laboratory studies have demonstrated that eye movement control training significantly improves reading performance. In the proposed study, we will translate our methods into clinical practice with a large sample of patients with central vision loss.

In Phase 1, we will develop a standardized, user-friendly, computer-based platform that will allow patients to easily self-administer training exercises. The software platform will be designed to automatically choose the appropriate exercises based on a patient's previous performance, run the training exercise, and collect performance data into a universal patient data file. In Phase 2, the platform will be tested in two settings: in standard clinical rehabilitation practice and in the patient's home. Reading outcomes in the two settings will be compared.

# Phase 1 – Development and Testing of the Platform for Administration of Eye Movement Control Training (PAECT)

The PAECT will be developed to allow patients to easily self-administer the exercises. We will design the interface to be accessible to users with low vision. Large icons, touch-sensitive displays, and/or voice controls will be used. The interface will be built, tested, and improved over the first year of the project.

# Phase 2 - Clinic-Based Versus Home-Based Training

In this phase, we will compare reading outcomes from training with PAECT in a low-vision clinic setting and with feedback on performance given by a rehabilitation therapist to training with the PAECT by the patients in their own homes. We have previously demonstrated in our laboratory experiments that eye movement training exercises increase reading speed, but we wish to know whether these findings can be extrapolated to clinical practice. The results of this study will allow us to quantify the role of direct support and feedback from the therapist during each session versus any advantages that may result from more frequent practice on the exercises afforded by having the equipment at home.

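### The Phase 2 claim to quantify therapist feedback versus extra home practice cannot be met: two arms that differ in several ways identify only the net programme difference

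*Combined protocol and SAP*

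**What the plan says.** The Phase 2 section states what the results will deliver: they will "quantify the role of direct support and feedback from the therapist during each session versus any advantages that may result from more frequent practice". Methods of Procedure puts the aim more modestly: "Reading outcomes in the two settings will be compared".

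The Procedure section describes the two arms.

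- **Clinic arm.** Patients "return at weekly intervals for two-hour PAECT training sessions", eight in total, "with feedback and encouragement given by the therapist".
- **Home arm.** Patients are told to "practice with the PAECT program as often as possible, but at least two hours per week". No upper limit is given.
- **Calls.** Directly after the home instructions comes: "Patients will receive weekly from calls from the Program Coordinator, who will answer technical questions". The coordinator will also "encourage frequent use of the program, but no feedback about performance will be given". The sentence does not say which arm it covers.
- **Duration.** The training period is "4 weeks of training, Month 1 assessment visit, 4 weeks of additional training".

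All patients receive instruction and training on Module 1 on Day 2, whichever arm they are in.

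Research Design and Statistical Analysis Plan provides a group-by-time repeated measures analysis over three assessments (baseline, Months 1 and 2). It contains no term for practice time, no summary of practice and no method for separating the components of the two programmes. Key Questions asks whether home training can be as effective as clinic training, and proposes to answer by looking at whether the greater opportunity to practise improves reading.

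**The concern.** The Phase 2 sentence promises a quantified comparison of two named ingredients, therapist feedback and extra practice. The design compares two whole programmes that differ in both ingredients and in at least one other respect, the setting. A difference between arms cannot then be assigned to feedback or to practice. A null difference cannot distinguish a trial in which both matter and cancel from one in which neither matters.

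What is at stake is interpretation. A home advantage could be reported as proof that practice outweighs feedback, or a null result as proof that therapist feedback is dispensable. The data could support neither statement. The phrase about more frequent practice also presumes that home patients will practise more than clinic patients. The design does not guarantee this, and the analysis section would not show whether it happened.

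**Working it through.** The plan gives no figure to reproduce on this point. The check is whether the promised quantities can be obtained from the two arms, followed by a count of the practice hours.

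**Step 1. Set the arms side by side** (from Procedure and Methods of Procedure).

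| Component | Clinic arm | Home arm |
|---|---|---|
| Performance feedback | yes, from the therapist | none |
| Practice | eight scheduled two-hour sessions | two hours a week or more, no maximum |
| Setting | clinic | home |
| Weekly coordinator calls | not stated | apparently yes, by position in the text |

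**Step 2. Write the between-arm contrast.** At a given follow-up visit, let F be the effect of feedback, P of any extra practice, S of the home setting and C of the calls. Assume for simplicity that they add. With m the common mean:

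- clinic mean = m + F
- home mean = m + P + S + C
- home − clinic = P + S + C − F

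If both arms receive the calls, C cancels and the contrast is P + S − F.

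**Step 3. Ask what can be recovered.**

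- F alone requires P + S + C to be known. It is not.
- P alone requires F, S and C to be known. They are not.
- P − F, the trade-off, requires S + C = 0. If calls go to both arms it still requires S = 0. Neither is tested or stated.
- Even if S and C were both zero, only P − F would be available, not the role of either ingredient.
- P + S + C − F, the net programme difference, is estimable from the randomised comparison.

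**Step 4. Do repeated visits help?** No. Months 1 and 2 each add one contrast of the same form, and each may have its own component effects. The baseline assessment precedes the arm-specific training and carries no information about the components. More patients would make the net difference more precise without splitting it.

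**Step 5. What a null result would mean.** The net difference is zero if all components are zero. It is also zero if F = P with S = C = 0, and if F exceeds P but S + C makes up the gap. These three cases have different implications for P and F but give the same expected contrast.

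**Step 6. Count the practice hours.**

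- Clinic, scheduled: 8 sessions × 2 h = 16 h.
- Home, instructed minimum: (4 + 4) weeks × 2 h = 16 h.
- Instructed minimum difference: 16 − 16 = 0 h, with no upper limit at home.

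This takes the eight sessions to be the weekly ones, which fits eight weeks of training. The documents do not say whether the Day 2 training counts among them. If it did, seven weekly sessions would remain, 7 × 2 = 14 h. Either way Day 2 is common to both arms, and the home figure is an instruction, not a delivered amount. Actual hours in either arm may fall short of the figure, and at home they may exceed it.

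**The case against.** The strongest reply is that the sentence closes a rationale paragraph and is not an endpoint or hypothesis. The same paragraph begins by defining the comparison as clinic training with feedback against training at home. On that reading, *versus* means a net trade-off, with home practice and home setting as one idea. The calls encourage use of the program, so part of their effect is a route to more practice. The therapist also gives encouragement, so that element is present in both arms. Finally, any trial of two bundled programmes has this property.

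Much of this is fair. The components are not sharply separate, and P, S and C are a convenient labelling. But the sentence says what the results will allow the investigators to quantify, and it credits the home advantage to practice frequency in particular. The net trade-off reading still needs P − F, which the setting contaminates. Bundling is acceptable when the claim is about the bundle; here the claim goes further.

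Three stronger readings might be inferred and are not supported.

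- **That the primary comparison is confounded.** It is not. Setting, practice and feedback are parts of the programmes being compared, and randomisation identifies their net effect.
- **That the calls certainly go to the home arm only.** Their position and content suggest so, but the text says only that patients receive them. The conclusion holds either way.
- **That practice time will not be captured.** Methods of Procedure says the platform will store performance data. Whether that includes session time is not stated. What can be said is that no summary of practice is planned.

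**Conclusion.** The point holds as a limit on what may be claimed. The trial identifies the net difference between the home and clinic programmes, one contrast at each follow-up visit. It cannot quantify the role of feedback, the benefit of practice, or the difference between them. This follows from the two-arm structure and does not depend on sample size or on who receives the calls. Additivity was assumed only to keep the algebra short; interactions between components would add further unknowns.

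The premise of more practice at home is also open. The scheduled and instructed figures are both 16 h, so any difference depends on what patients choose to do.

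The wording and the reporting should be corrected. The arms, the randomisation and the group-by-time analysis can stay as they are. A factorial design would be needed only if separating the ingredients were a real objective, and the primary question does not require it.

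**What to change.** 1. **Restate the claim in the Phase 2 section.** For example: *The results will estimate the net effect on reading of the home programme compared with the clinic programme, each taken as a whole. The study does not separate the contributions of feedback, amount of practice and setting.* Read the sentence on opportunity for practice under Key Questions the same way, as a feature of the home programme and not as a separately estimated cause.
2. **Clarify the calls in Procedure.** State which arm or arms receive them, and describe the two programmes accordingly. If only one arm does, add calls to the list of components that are not separated.
3. **Record and report practice.** Have PAECT log session time in the patient data file in both arms. In the analysis section, pre-specify a descriptive summary of total training hours per patient by arm: for example median, quartiles, range and the proportion below 16 h. State whether Day 2 is counted. Label any analysis relating hours to reading speed as exploratory, because hours are self-selected. Such an analysis cannot restore the feedback-versus-practice claim.

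The cost is a narrower stated claim, one clarification, one logged field and one table. The field should be cheap if the software is still being built. The Phase 1 section places that work in the first year, but the documents do not give its current status. If the software is fixed and cannot log time, a practice diary is a less reliable substitute.
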